  - Absolute neutrophil count (ANC)  $<1500 \text{ u/L} (1 \times 10^9/\text{L}).$
  - Platelets  $<100 \times 10^3$  u/L (after at least 3 days without platelet transfusion).
  - Hemoglobin <9 g/dL or <5.6 mmol/L (without transfusions within 2 weeks of initiation of IMP).
  - Total bilirubin >2 upper limit of normal (ULN).
  - AST and/or ALT > 3 × ULN (or > 5 × ULN for patients with liver metastases).
  - Estimated glomerular filtration rate (eGFR) <30 mL/min/1.73 m^2 (Modified Diet in Renal Disease [MDRD] Formula; Appendix H).

- E 21. Women of reproductive potential and male subjects with female partners of childbearing potential who are not willing to avoid pregnancy 2 weeks before and during the study treatment period and for 6 months following discontinuation of study treatment by using effective contraceptive methods such as:
  - Diaphragm and spermicide PLUS male condom, or
  - Intrauterine device PLUS male condom, or
  - Medical method (such as hormonal contraceptive) PLUS male condom.
  - A woman of productive potential is a woman who: 1) has achieved menarche at some time point, 2) has not undergone a hysterectomy or bilateral oophorectomy or 3) has not been naturally postmenopausal (amenorrhea following cancer therapy does not rule out childbearing potential) for at least 24 consecutive months (ie, has had menses at any time in the preceding 24 consecutive months). The choice of effective method is left to Investigator judgment, in accordance to local regulation. Sterilized or infertile subjects are exempted from the requirement to use of contraception. In order to be considered sterilized or infertile, subjects must have undergone surgical sterilization (vasectomy/bilateral tubectomy, hysterectomy, bilateral ovariectomy) or be a postmenopausal woman defined as 12 months or more with no menses prior to enrollment and 50 years of age. True abstinence is acceptable when this is in line with the preferred and usual lifestyle of the patient. Periodic abstinence (eg, calendar, ovulation, symptothermal, postovulation methods) and withdrawal are not acceptable methods of contraception.
- E 22. Pregnant or breastfeeding woman or woman who intends to become pregnant during the participation in the study.
- E 23. Known intolerance or hypersensitivity to any component of isatuximab and/or REGN2810.

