# 8.9.2 Contraceptive measures and pregnancy counseling

Females of child bearing potential or male patients with female partners of childbearing potential shall be required to use effective contraceptive methods (double barrier method, intrauterine device, oral contraception or abstinence) 2 weeks prior to first study treatment, while on therapy and for 6 months following the last dose of study treatment.

A woman is considered of childbearing potential (WOCBP), ie, fertile, following menarche and until becoming postmenopausal unless permanently sterile.

The following highly effective methods of contraception are accepted:

- Sexual abstinence.
- Diaphragm and spermicide PLUS male condom, or,
- Intrauterine device PLUS male condom, or,
- Medical method (such as hormonal contraceptive) PLUS male condom.

The choice of effective method is left to Investigator judgment, in accordance to local regulation. Sterilized or infertile patients are exempt from the requirement to use of contraception. In order to be considered sterilized or infertile, patients must have undergone surgical sterilization (vasectomy/bilateral tubectomy, hysterectomy, bilateral ovariectomy) or be a postmenopausal woman defined as 12 months or more with no menses prior to enrollment and 50 years of age.

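### The contraception exemption at 12 months without menses and age 50 drops E 21's own warning about periods that stop after cancer therapy

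*Protocol*

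**What the plan says.** E 21 (Clinical Trial Summary and Section 7.3) excludes women of reproductive potential who are unwilling to avoid pregnancy, and male patients with partners of childbearing potential on the same terms. Its definition of such a woman has three limbs. The third turns on her not having been "naturally postmenopausal (amenorrhea following cancer therapy does not rule out childbearing potential) for at least 24 consecutive months", explained as meaning that she "has had menses at any time in the preceding 24 consecutive months".

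Later in the same criterion: "Sterilized or infertile subjects are exempted from the requirement to use of contraception". Those exempt include women with surgical sterilization and a "postmenopausal woman defined as 12 months or more with no menses prior to enrollment and 50 years of age". This second rule does not ask why menses stopped.

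Section 8.9.2 repeats the 12-month/age-50 exemption and gives the definition behind the abbreviation used for testing: "A woman is considered of childbearing potential (WOCBP), ie, fertile, following menarche and until becoming postmenopausal unless permanently sterile". It has no 24-month rule and no caution about cancer therapy. Sections 12.2 to 12.5 require pregnancy tests for WOCBP. The pregnancy-test footnotes of Sections 1.3 and 1.4 use the unabbreviated term and cite no definition.

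On methods, the first sentence of Section 8.9.2 requires patients to "use effective contraceptive methods (double barrier method, intrauterine device, oral contraception or abstinence"). Its list of accepted methods instead has "Intrauterine device PLUS male condom", and likewise a condom in addition to any medical method. E 21 names the same paired methods.

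**The concern.** E 21 singles out one group as unsafe to assume infertile: women whose periods stopped after cancer therapy. The exemption that follows takes in many of those same women once they are 50 and have had 12 months without menses. This trial recruits from that group. I 15 allows one prior chemotherapy regimen for advanced NSCLC, and I 14 requires a later or concurrent anti-PD-1/PD-L1 regimen, so a year or more may pass between the start of chemotherapy and enrollment.

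At stake is fetal exposure to either antibody. The remaining safeguards are the exclusion of pregnant women (E 22), pregnancy as an event of special interest (Section 10.5.5) and stopping treatment on pregnancy (Section 11). All three act only once a pregnancy is known. Without scheduled tests, it may be known late.

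The mismatch on methods in Section 8.9.2 is a separate matter. It reaches every patient under the contraception duty, because a site following the opening sentence would accept an intrauterine device or the pill without a condom.

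**Working it through.** No sample-size or error-rate formula bears on this point. The check sets the rules side by side and then counts the tests that hang on the classification.

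**Reading assumptions.** The age limit is taken as 50 or over, although the text gives only the number. The limbs of the E 21 definition are taken as cumulative. Literally the text joins them with an or: "has not undergone a hysterectomy or bilateral oophorectomy or 3) has not been naturally postmenopausal". Taken at its word, that would make almost every woman of reproductive potential.

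**Rules applied to women of 50 or over**

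| Amenorrhea | E 21 definition | Exemption (E 21 and 8.9.2) |
|---|---|---|
| Natural, 12 to under 24 months | Reproductive potential | Exempt |
| Natural, 24 months or more | None | Exempt |
| After cancer therapy, 12 to under 24 months | Reproductive potential | Exempt; caution absent |
| After cancer therapy, 24 months or more | Unclear: the word naturally and the caution point one way, the 24-month gloss the other | Exempt; caution absent |

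Under 50 the exemption does not apply, so the gap does not arise. Take a 51-year-old with 14 months of amenorrhea since chemotherapy. E 21's definition and caution place her among women who may conceive; the exemption releases her from contraception. Under Section 8.9.2 she is postmenopausal, hence not WOCBP, hence not tested.

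**Scheduled tests that depend on the label.** From the pregnancy-test footnote of Section 1.3: one serum test before the first dose, one test on Day 1 of each 21-day cycle, one at end of treatment (30 days after the last dose), then every 30 days to 6 months. Taking 6 months as 180 days, the post-treatment tests fall at 30, 60, 90, 120, 150 and 180 days, which is 6. For n cycles:

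T(n) = 1 + n + 6

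- 1 cycle: 1 + 1 + 6 = 8
- 6 cycles: 1 + 6 + 6 = 13
- Two years (730 days): the 35th Day 1 falls on day 1 + 34 × 21 = 715 and the 36th would fall on day 736, so n = 35 and T = 1 + 35 + 6 = 42

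If she is not classed as of childbearing potential, the count is 0.

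**Who can be affected.** Among patients, only those with NSCLC can be women: Cohort B (36), Cohort D if opened (36), at most 36 + 36 = 72 of both sexes, plus any Phase 1 NSCLC patients not counted in Cohort B. The documents give no split by sex, age or menopausal history, so no smaller figure can be derived. The same definition also decides the status of female partners of male patients, mCRPC patients included. Partners have no scheduled tests, so for them only contraception is affected, and the caution matters only if the partner has herself had cancer therapy.

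**The case against.** The strongest reply is that E 21 does not contradict itself. It states a general definition and then an exemption, and an exemption presupposes someone who would otherwise be caught. Bilateral tubectomy works the same way: it is missing from the definition, appears only in the exemption, and nobody would call that a conflict. This stands. A reader might infer that the 24-month and 12-month rules clearly conflict and that two sites could reach opposite decisions on excluding the same woman. The wording of the exemption does not support that; for contraception it prevails.

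A reader might also infer that no definition governs the pregnancy-test footnotes. That goes too far as well. The list of abbreviations expands WOCBP to the footnotes' own term, Section 12.3.1 carries nearly the same sentence as the footnotes with the abbreviation in place, and Section 8.9.2 defines it. The missing cross-reference is a drafting gap, not an open question of substance.

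Neither reply removes the remaining problem. Read in this orderly way, the plan gives a definite answer for women of 50 or over with therapy-induced amenorrhea, no contraception and no scheduled tests, and that answer is the one E 21's caution warns against.

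The opposing case also notes that the affected women are few, aged about 50 or over and ill with advanced NSCLC. That is fair, and it limits the weight of the point.

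**Conclusion.** The point holds as a minor safety-wording correction. The caution about amenorrhea after cancer therapy appears in E 21's definition but not in the exemption that overrides it, nor in Section 8.9.2, which most naturally decides who is tested. A woman in this group loses the contraception duty and 8 to 42 scheduled tests, depending on time on treatment. The number of such women cannot be computed from the documents and is probably small.

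This rests on reading the age limit as 50 or over, the exemption as a deliberate carve-out, and Section 8.9.2 as the source of the WOCBP definition.

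It would be tempting to treat 24 months as the protocol's own limit for therapy-induced amenorrhea. The documents do not settle that: the 24 months attach to natural menopause, and the caution carries no time limit.

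The contradiction on methods within Section 8.9.2 is real and independent, though the list of accepted methods in the same section shows the likely intent. Nothing here touches sample size, stage boundaries or analysis.

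**What to change.** - In the E 21 exemption (Clinical Trial Summary and Section 7.3) and in Section 8.9.2, state that the 12-month/age-50 rule applies only to natural amenorrhea and that amenorrhea following cancer therapy does not qualify. Any time limit after which such a woman may be regarded as infertile should be set by the sponsor's clinicians.
- Use this one definition for WOCBP, for patients and for partners, and cross-reference it in the pregnancy-test footnotes of Sections 1.3 and 1.4. While there, join the limbs of the E 21 definition with and.
- Make the first sentence of Section 8.9.2 agree with its list of accepted methods.

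Amended Protocol 05 already revised Section 8.9.2 and the pregnancy-test schedule, in part to match E 21 on the duration of contraception; this would align who is covered as well. It is text only and can go into the next amendment, with ethics committee approval as Section 17 requires. The cost is that a probably small, not computable number of extra women would need contraception and pregnancy tests, for example 13 tests each over 6 cycles and at most 42 over two years.

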# 8 STUDY TREATMENTS

#### 8.1 INVESTIGATIONAL MEDICINAL PRODUCT

# 8.1.1 Isatuximab (SAR650984)

#### 8.1.1.1 Pharmaceutical form

The drug product is presented as a concentrate for solution for infusion in vials containing 20 mg/mL (500 mg/25 mL) isatuximab in 20 mM histidine, 10% (w/v) sucrose, 0.02% (w/v) polysorbate 80 and pH 6.0 buffer.

Isatuximab is supplied as a sterile, non-pyrogenic, injectable, and colorless, 20 mg/mL concentrate for solution for infusion that may contain white to off-white particulates and is packaged in 30 mL glass vials fitted with elastomeric closure. Each vial contains a nominal content of 500 mg of isatuximab. The fill volume has been established to ensure removal of 25 mL.

For administration to patients, the appropriate volume of isatuximab will be diluted in an infusion bag of 0.9% sodium chloride solution or 5% dextrose solution. The final infusion volume corresponding to the dose of isatuximab will be administered for a period of time that will depend on dose administered and on the amount of protein given per hour.

#### 8.1.1.2 Dose of drug per administration

The starting dose of isatuximab is 10 mg/kg (see Section 6.2.1).

#### 8.1.1.3 Preparation, reconstitution and administration

Isatuximab concentrate for solution for infusion will be diluted in an infusion bag with 0.9% sodium chloride solution or 5% dextrose solution to achieve the appropriate drug concentration for infusion.

Infusion via a central line is preferred if available. In case of patients with local intolerance after peripheral IV infusion, the decision to use a central line is left to the Investigator. The final infusion volume corresponding to the dose of isatuximab will be administered by IV infusion for the period of time that depends on total dose administered.

Prior to dosing, each patient's dose will be individually prepared by the study pharmacist and labeled with the protocol number, patient number, and treatment description. The patient's weight should be measured prior to each treatment to allow calculation of the isatuximab dose.

For infusion, an IV tubing administration set with a  $0.20 \,\mu m$  in-line filter will be used; if an in-line filter is unavailable, a  $0.20 \,\mu m$  filter unit may be attached to the administration set before administration. Further details are provided in the Pharmacy Manual.

# 8.1.2 REGN2810 (SAR439684)

#### 8.1.2.1 Pharmaceutical form

REGN2810 drug product is presented as a concentrate for solution for infusion of 50 mg/mL in 10 mL vials with 5.0 mL withdrawable, containing 10 mM histidine, 5% (w/v) sucrose, 1.5% (w/v) L-proline, and 0.2% (w/v) polysorbate 80, at pH 6.0.

# 8.1.2.2 Dose of drug per administration

The starting dose of REGN2810 is 350 mg per administration (see Section 6.2.1).

#### 8.1.2.3 Preparation, reconstitution and administration

REGN2810 concentrate for solution for infusion will be diluted in an infusion bag with 0.9% sodium chloride solution to achieve the appropriate drug concentration for infusion.

Infusion via a central line is preferred if available. In case of patients with local intolerance after peripheral IV infusion, the decision to use a central line is left to the Investigator. The final infusion volume corresponding to the dose of REGN2810 will be administered by IV infusion for the period of time that will depend on total dose administered.

Prior to dosing, each patient's dose will be individually prepared by the study pharmacist and labeled with protocol number, patient number, and treatment description.

For infusion, an IV tubing administration set with a  $0.20~\mu m$  in-line filter will be used; if an in-line filter is unavailable, a  $0.20~\mu m$  filter unit may be attached to the administration set before administration. Further details are provided in the Pharmacy Manual.

# 8.2 NONINVESTIGATIONAL MEDICINAL PRODUCT(S)

Patients should routinely receive premedication 30 to 60 minutes prior to the start of the isatuximab infusion (no longer than 60 minutes) to reduce the risk and severity of IARs commonly observed with monoclonal antibodies. See Section 4.4.4 for additional information on premedication requirements.

- The recommended premedication agents are listed below: Acetaminophen (paracetamol) 650 to 1000 mg, taken orally.
- Ranitidine 50 mg IV or equivalent.
- Diphenhydramine 25 to 50 mg IV or equivalent.
- Methylprednisolone 100 mg IV or equivalent.
- Montelukast 10 mg orally or equivalent

Non-investigational products will be locally sourced and formulations may vary. Investigators must follow the Summary of Product Characteristics/Package Inserts in terms of contraindications for non-investigational medicinal products (NIMPs).

# 8.2.1 Acetaminophen (paracetamol)

Commercial supplies of acetaminophen or equivalent will be used for this study. Please refer to the package insert for further details as regards to formulation, storage and handling purposes.

# 8.2.2 Ranitidine or equivalent

Ranitidine is presented as a solution for IV infusion. Commercial supplies of ranitidine or equivalent will be used for this study. Please refer to the package insert for further details as regards to formulation, storage and handling purposes. Equivalents are other approved H2 antagonists (eg, cimetidine), oral proton pump inhibitors (eg, omeprazole, esomeprazole).

# 8.2.3 Diphenhydramine or equivalent

Diphenhydramine is presented as a solution for IV infusion. Commercial supplies of diphenhydramine or equivalent will be used for this study. Please refer to the package insert for further details as regards to formulation, storage and handling purposes. Equivalents are, eg, cetirizine, promethazine, dexchlorpheniraminem according to local approval and availability. Intravenous route is preferred for at least the first 4 infusions.

#### 8.2.4 Methylprednisolone or equivalent

Methylprednisolone is presented as a solution for IV infusion. Commercial supplies of methylprednisolone or equivalent will be used for this study. Please refer to the package insert for further details as regards to formulation, storage and handling purposes.

#### 8.2.5 Montelukast

Commercial supplies of montelukast will be used for the study. Please refer to the package insert for further details as regards to formulation, storage and handling purposes.

#### 8.3 DOSING SEQUENCE

#### 8.3.1 Study treatment

All patients will receive isatuximab in combination with REGN2810 for Phase 1 (safety run-in) and isatuximab only or isatuximab in combination with REGN2810 for Phase 2 (efficacy signal).

Emergency equipment and medication for the treatment of IARs (eg, antihistamines, bronchodilators, IV saline, corticosteroids, acetaminophen, and/or epinephrine) must be available for immediate use.

A table showing planned study treatment administration is provided in Section 1.2.

Property of the Sanofi Group - strictly confidential

Page 85

#### Phase 1 and Phase 2 Cohort A-1 and B:

On Day 1 of each cycle (C1 to Cn) patients will receive:

• Premedications as described in Section 8.2

followed by

• REGN2810 infusion over 30 minutes

followed by

• Isatuximab IV infusion over approximately 2 to 4 hours.

In Cycle 1 Day 8 and 15, patients will receive:

• Premedications as described in Section 8.2

followed by

• Isatuximab IV infusion over approximately 2 to 4 hours.

#### Phase 2 Cohort A-2

On Day 1 of each cycle (C1 to Cn) patients will receive:

• Premedications as described in Section 8.2

followed by

• Isatuximab IV infusion over approximately 2 to 4 hours.

In Cycle 1 Day 8 and 15, patients will receive:

• Premedications as described in Section 8.2

followed by

• Isatuximab IV infusion over approximately 2 to 4 hours.

# Phase 2 Cohort C

On Day 1 of each cycle (C1 to Cn) patients will receive:

• Premedications as described in Section 8.2

followed by

• REGN2810 infusion over 30 minutes (not applicable if isatuximab monotherapy is administered)

followed by

• Isatuximab IV infusion over approximately 2 to 4 hours.

#### Phase 2 Cohort D

On Day 1 of each cycle (C1 to Cn) patients will receive:

• Premedications as described in Section 8.2

followed by

• REGN2810 infusion over 30 minutes

followed by

• Isatuximab IV infusion over approximately 2 to 4 hours.

#### 8.3.1.1 Rate and duration of infusion

The duration of infusion for REGN2810 350 mg is 30 minutes per administration.

For isatuximab, the rate of infusion should be initiated at 175 mg/hour:

- First infusion: initiate infusion at 175 mg/hour. In the absence of IARs after 1 hour of infusion, increase infusion rate by 50 mg/hour increments every 30 minutes, to a maximum of 400 mg/hour.
- Subsequent infusions: initiate infusion at 175 mg/hour. In the absence of IAR after 1 hour of infusion, increase rate by 100 mg/hour increments every 30 minutes, to a maximum of 400 mg/hour.

Guidelines for patients who develop IARs are provided in Section 6.6.5.

#### 8.4 BLINDING PROCEDURES

This is an open-label study; therefore, blinding procedures are not applicable.

#### 8.5 METHOD OF ASSIGNING PATIENTS TO TREATMENT GROUP

All eligible patients will be enrolled into the Phase 1 (safety run-in) of the study. Any proportion of patients with each tumor type can be enrolled.

Patients who received the RP2D in Phase 1 and new patients will then enter the Phase 2 part of Cohort A-1 and Cohort B depending on the type of tumor. If the decision is made to initiate the mCRPC Cohort A-1 Phase 2 Stage 2, an isatuximab monotherapy cohort (Cohort A-2) will be initiated for patients with mCRPC. Patients with mCRPC will be randomly assigned in a 1:1 randomization ratio to Cohort A-1 (Phase 2 Stage 2; isatuximab plus REGN2810 combination therapy) or Cohort A-2 (Phase 2 Stage 1; isatuximab monotherapy).

Study treatment should be initiated within 3 working days after enrollment.

If the decision is to initiate Cohort C and/or Cohort D, patients will be assigned depending on the type of tumor.

#### 8.6 INVESTIGATIONAL MEDICINAL PRODUCT PACKAGING AND LABELING

#### 8.6.1 Isatuximab

Isatuximab is packaged in 30 mL glass vials fitted with elastomeric closure. Packaging is in accordance with the administration schedule.

The content of the labeling is in accordance with the local regulatory specifications and requirements.

#### 8.6.2 REGN2810

REGN2810 is packaged in USP Type 1 clear glass, 10 mL vial with 20 mm gray chlorobutyl rubber stopper with FluroTec® coating and 20 mm red flip-off seal. Packaging is in accordance with the administration schedule.

The content of the labeling is in accordance with the local regulatory specifications and requirements.

#### 8.7 STORAGE CONDITIONS AND SHELF LIFE

#### 8.7.1 Isatuximab

Investigators or other authorized persons (eg, pharmacists) are responsible for storing isatuximab in a secure and safe place with restricted access in accordance with local regulations, labeling specifications, policies, and procedures.

Control of isatuximab storage conditions, especially control of temperature (eg, refrigerated storage), and information on in-use stability and instructions for handling the Sanofi compound should be managed according to the rules provided by the Sponsor.

Isatuximab is to be stored at  $+2^{\circ}$ C to  $+8^{\circ}$ C (36°F to 46°F), protected from light. All vials must be kept in their box until use. No protection from light is required for storage in the infusion bags.

Details of the storage conditions for the diluted solution are provided in the Pharmacy Manual.

